5. STUDY TREATMENTS

For the purposes of this study, and per International Conference on Harmonisation (ICH) guidelines, investigational product is defined as a pharmaceutical form of an active ingredient including a product with a marketing authorization when used or assembled (formulated or packaged) in a way different from the approved form, or when used for an unapproved indication, or when used to gain further information about an approved use (ICH E6 1.33).

For this study, the investigational product is bosutinib.

5.1. Allocation to Treatment

Registration will be performed centrally by the sponsor for all patients. Following full assessment and determination that the patient meets all eligibility criteria, the investigator or designee will fax or email a complete Registration Form to the designated sponsor study team member. The sponsor will assign a patient identification number, which will be used on all Case Report Form (CRF) pages and other trial-related documentation or correspondence referencing that patient and fax or email to the site.

No patient shall receive study drug until the investigator or designee has received the following information from the sponsor: confirmation of the patient's enrollment.

5.2. Patient Compliance

For self-administration of bosutinib at home, compliance will be captured and completed by the patient.

A patient diary will be provided to the patients to aid in patient compliance with the dosing instructions. The diary will be maintained by the patient to include missed or changed bosutinib doses. Patients will be required to return all bottles of bosutinib every visit. The number of bosutinib tablets remaining will be documented and recorded at each visit. The patient diary may also be used to support this part of the bosutinib accountability process.

5.3. Investigational Product Supplies

5.3.1. Dosage Form(s) and Packaging

Bosutinib tablets (100 mg dosage strength) will be supplied by Pfizer in high-density polyethylene (HDPE) bottles. The bosutinib commercial formulation will be supplied in this study. Bosutinib will be labeled according to local regulations.

5.3.2. Preparation and Dispensing

The study treatment should be dispensed at each visit per the schedule of treatment. A qualified staff member will dispense the investigational product in the bottles provided, in quantities appropriate for the study visit schedule. The patient/caregiver should be instructed to maintain the product in the bottle provided throughout the course of dosing, keep the investigational product away from children, and return the bottle to the site at the next study visit.

5.4. Administration

The starting dose is 400 mg QD, orally, recommended to be taken in the morning with a meal and approximately 200 mL of water. Available data show that both tolerance and absorption are greatly improved by taking bosutinib with a meal, including adequate dietary fats; no restriction is imposed on patients' food choices.

Patients will swallow the investigational product whole and will not manipulate or chew the investigational product prior to swallowing. Patients must be instructed that should they miss a dose or vomit any time after taking a dose, they must not "make it up" with an extra dose. Instead, resume the subsequent doses as originally prescribed. Any missed dose may be taken up to 12 hours prior to the next scheduled dose, otherwise it should be skipped and dosing resumed with subsequent doses as prescribed.

On PK sampling days, the bosutinib dose should be taken in the hospital under the supervision of the study site personnel. The bosutinib dose should be administered after the 0 hour (pre-dose) PK sample has been collected.

Dosing is continuous without planned interruptions; patients who complete 12 months (48 weeks) Core Treatment Phase will continue dosing without interruption into the Extension Phase. Each patient will receive daily bosutinib for up to approximately 3 years after registration of last patient (12 months [48 weeks] Core Treatment Phase and the following ≥ 24 months [96 weeks] Extension Phase) or until the end of the study, treatment failure, unacceptable toxicity, death, or withdrawal of consent, whichever occurs first.

In this study, the dose of bosutinib may be escalated for unsatisfactory response or reduced for toxicity. Dose modifications (as summarized in Table 1) may be performed according to the criteria as summarized in detail in Section 5.4.1 and Section 5.4.2. For dose increases, the investigator must communicate directly with the patient and an additional ad hoc visit should be considered so as not to postpone the start of optimized dosing.

Table 1. Dose Modifications for Bosutinib

Dose Level	Bosutinib (mg)
Second Dose Increase (+2)	600
First Dose Increase (+1)	500
Starting Dose	400
First Dose Decrease (-1)	300
Second Dose Decrease (-2)	200*

*subject to sponsor approval

5.4.1. Dose Escalation

Patients should have their dose increased to 500 mg QD and further up to a maximum of 600 mg QD of bosutinib, as tolerated, if all of the following criteria are met:

- a. They do not demonstrate an optimal response at Month 3 (ie, BCR-ABL transcripts $>10\%$ and/or Ph+ metaphases $>35\%$)

- b. They have no Grade 3/4 adverse events at the time of dose escalation, and all prior Grade 3/4 events have resolved to Grade 1/2 as follows:
- All Grade 3/4 hematologic toxicities have resolved to Grade ≤ 1 .
 - All Grade 3/4 non-hematological toxicities have resolved to Grade ≤ 2 and are manageable with supportive therapy. Grade 3/4 non-hematological toxicities resolved to Grade ≤ 2 which would be acceptable for dose escalation are: vomiting, nausea, abdominal pain, rash, headache, myalgia and fatigue. All other non-hematological toxicities should be Grade ≤ 1 for dose escalation.
 - In addition, for dose escalation to be permitted in a patient who has experienced such toxicities (ie, Grade 3/4 hematologic and non-hematologic), the patient must have been able to be successfully re-challenged (ie, not have experienced recurrence of that toxicity at the Grade 3/4 level) at the lower dose after recovery from the Grade 3/4 toxicity.

AND

- c. All Grade 2 non-hematologic toxicities have resolved to Grade ≤ 1 .

All responses will be assessed per protocol at Month 3 for the purpose of dose escalation to support response. If all of the above criteria are met, dose of bosutinib will be increased.

At Month 6, it is recommended that the investigator follow existing CML guidelines (ELN or NCCN, see [Appendix 2](#)) to determine if dose escalation is indicated based upon failure to demonstrate an optimal response; however, the protocol does not mandate a dose increase; the decision is left to the clinical judgment of the investigator, taking into account local guidelines. The same safety criteria apply as for the Month 3 dose escalation.

At any time, if the patient loses a complete hematologic or complete cytogenetic response, or has a confirmed loss of MMR and a $5 \times$ PCR increase, then a 1-level dose increase, up to a maximum of 2 dose levels, is suggested, after consultation with the sponsor. In addition, cytogenetic assessment on bone marrow should be reintroduced in the presence of loss of MMR and a $5 \times$ PCR increase and until MMR is achieved again. The same safety criteria apply as for the Month 3 dose escalation.

Lack of response for dose escalation (mandatory at Month 6, and recommended at Month 3) is defined as: BCR-ABL transcripts $>10\%$ by qPCR IS and/or Ph⁺ metaphases $>35\%$.

Additionally, anytime lack of optimal response is demonstrated, a BCR-ABL mutation test must be performed on the same sample if possible.

The BCR-ABL transcript levels (and mutation analyses when appropriate) will be assessed by a central laboratory throughout this study.

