6.2. Core Treatment Phase

For Core Treatment Phase procedures, see [SCHEDULE OF ACTIVITIES](#) table and [ASSESSMENTS](#) section.

Patients will have visits at the study site on Day 1 and Weeks 1, 2, 3, 4, 6, 8, 10, 12, 16, 20, and 24, then every 12 weeks for the first year of treatment in the 12 months (48 weeks Core Treatment Phase). Additional visits may be required for patients requiring dose increases at the Week 12 and Week 24 visits, these will be performed as soon as possible and within 4 weeks of the result requiring dose change being known. Patients not requiring a dose change will be contacted by telephone.

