Appendix 2. Response Definitions

A. Hematologic Responses to Treatment

Hematologic Responses	Definition
Complete Hematologic Response (CHR) had to meet all criteria	
 • WBC $\leq 10 \times 10^9/L$ • Basophils <5% in blood • No myelocytes, promyelocytes, myeloblasts in the blood differential • Platelet count $<450 \times 10^9/L$ • Spleen non-palpable^a

a. In a statistical analysis, if spleen disease was not assessed, it is assumed that spleen is non-palpable.

B. Cytogenetic Responses to Treatment

Before Treatment	Cytogenetic Responses (based on analysis of at least 20 metaphases)	% Philadelphia Chromosome Positive Cells
Chronic Phase	None	>95%
	Minimal	66-95%
	Minor	36-65%
	Partial	1-35%
	Complete	0%
	Major	Complete + Partial Rates

C. Molecular Responses to Treatment

Before Treatment	Molecular Response	RT-PCR (BCR-ABL Ratio)
Chronic Phase	Major, or MMR	≤0.1% (corresponding to ≥3 log reduction from baseline*) with a minimum number of ABL transcripts specified by the central laboratory
	MR ¹	A 1 log reduction in BCR-ABL transcript with a minimum number of ABL transcripts specified by the central laboratory
	MR ²	A 2 log reduction in BCR-ABL transcript with a minimum number of ABL transcripts specified by the central laboratory
	MR ^{4.0}	Either (i) Detectable disease with ≤0.01% BCR-ABL IS or (ii) Undetectable disease in cDNA with a minimum number of ABL transcripts specified by the central laboratory
	MR ^{4.5}	Either (i) Detectable disease with ≤0.0032% BCR-ABL IS or (ii) Undetectable disease in cDNA with a minimum number of ABL transcripts specified by the central laboratory in the same volume of cDNA used to test for BCR-ABL

* standardized baseline from central laboratory

D. Definitions of Blast Phase and Accelerated Phase

Patient meeting any of the following criteria:

Blast Phase	≥30% Blasts in blood or bone marrow Extramedullary blast proliferation, other than in spleen
Accelerated Phase	15-29% blasts in blood or marrow, or >30% blasts plus promyelocytes in blood or marrow with blasts <30%; ≥20% basophils in blood Persistent thrombocytopenia (<100 × 10 ⁹ /L) unrelated to therapy ^a Clonal chromosome abnormalities in Ph ⁺ cells (CCA/Ph ⁺), major route, on treatment ^b

a. In a statistical analysis, persistent thrombocytopenia is not considered to define AP progression as the database does not collect data regarding the relationship between the platelet value and therapy.

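### Protocol Section 5.4.1 makes a Month 6 dose increase for lack of response both discretionary and mandatory, and is less sharply inconsistent on Month 3

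*Protocol*

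**What the plan says.** Protocol Section 5.4.1 deals with escalation for inadequate response in two places.

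The main rule is built on Month 3. It opens with "Patients should have their dose increased to 500 mg QD and further up to a maximum of 600 mg QD of bosutinib, as tolerated", subject to a list of criteria: a response short of optimal at Month 3, and toxicity conditions. It then adds "If all of the above criteria are met, dose of bosutinib will be increased". For Month 6 the text changes register: "At Month 6, it is recommended that the investigator follow existing CML guidelines (ELN or NCCN, see" Appendix 2), and then "the protocol does not mandate a dose increase; the decision is left to the clinical judgment of the investigator". The Month 3 safety criteria carry over to Month 6.

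Further down the same section, the definition of lack of response begins "Lack of response for dose escalation (mandatory at Month 6, and recommended at Month 3) is defined as" and gives one threshold for both visits: BCR-ABL transcripts above 10%, Ph+ metaphases above 35%, or both.

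Both statements are current protocol text, not entries in the summary of changes.

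**The concern.** A site cannot treat the same Month 6 decision as left to judgment and as compulsory. Two investigators with identical patients could act differently, each able to cite Section 5.4.1. A monitor would have no basis for deciding whether a patient who was not escalated is a protocol deviation.

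The decision falls between the start of treatment and the Week 48 MMR assessment, so it affects the dose under which the primary endpoint is observed. Two other sections refer back to it. Section 6.5 makes treatment-failure conditions depend on escalation having taken place as Section 5.4.1 specifies, or on adverse events having ruled it out. Section 7.1.1 lists lack of response after escalation among the triggers for mutation testing.

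**Working it through.** The point is textual, so the check sets the statements side by side, looks for text that settles them, and then measures the possible difference in exposure.

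**Step 1. The two statements.**

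| Visit | Month 3 and Month 6 paragraphs | Lack-of-response definition | Compatible? |
|---|---|---|---|
| Month 3 (Week 12) | Should increase as tolerated; then stated as something that will happen if all criteria are met | Recommended | Tension in strength only |
| Month 6 (Week 24) | Not mandated; investigator's judgment under guidelines | Mandatory at a fixed threshold | No |

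At Month 3 both texts favour an increase and the threshold is the same, so they part only if an investigator declines. At Month 6 they are opposed.

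**Step 2. Does other text decide it?**

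- Section 5.4: "In this study, the dose of bosutinib may be escalated for unsatisfactory response or reduced for toxicity". This is permissive and names no visit. Section 3.1 is similar, and SAP Section 2.2 says only that escalation is allowed.
- Section 6.2: "Additional visits may be required for patients requiring dose increases at the Week 12 and Week 24 visits". This covers both visits without saying at which one an increase is compulsory.
- Appendix 2, cited in the Month 6 paragraph, is headed "Appendix 2. Response Definitions". It contains hematologic, cytogenetic and molecular response definitions and the accelerated and blast phase criteria. It has no Month 6 milestone.

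None of these settles which statement governs.

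**Step 3. Exposure at stake at Month 6.** Take a patient not increased before, above the threshold at Week 24, meeting the safety criteria and remaining on treatment to Week 48.

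- Not escalated, as the Month 6 paragraph permits: 0 weeks on an increased dose before Week 48.
- Escalated at once, as the definition requires: 48 − 24 = 24 weeks.
- Section 6.2 allows up to 4 weeks once the result is known: 48 − 24 − 4 = 20 weeks. Laboratory turnaround is not given and would shorten this further.

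The contrast is therefore 0 against at most about 24 weeks.

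**Step 4. Does any analysis rule use the escalation condition?**

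- Analysis sets (SAP Section 4) depend on dosing, Ph status and transcript type.
- The primary endpoint (SAP Sections 5.3.1.1 and 6.1.1.1) depends on MMR at Week 48, with a rule for a missing assessment.
- EFS (Protocol Section 9.2.2.4, SAP Section 3.2.4) lists death, transformation, loss of CHR, loss of CCyR and WBC doubling, with no reference to escalation.
- Dose escalation appears in SAP Section 6.5.3 only as a descriptive exposure summary: escalation to 500 and 600 mg, number of escalations and time to the first.

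**The case against.** The best rescue is to read the parenthesis in the definition as describing when response is assessed, not when the dose is raised. It does not work. The phrase is tied to escalation, and assessment at Month 3 is not merely recommended: Section 5.4.1 requires it, and the Schedule of Activities places RT-qPCR at both Weeks 12 and 24.

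Several limits on the point do stand.

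- The Month 3 difference is mild. The governing sentence there is itself advisory and qualified by tolerance, which is close to a recommendation. A reader might infer that the two statements are exact opposites at both visits; only Month 6 supports that.
- A reader might infer that the two statements set different Month 6 thresholds. The documents cite the guidelines without reproducing their milestones, so this cannot be shown. The Appendix 2 pointer may have been meant only for response definitions, in which case it needs only a citation correction.
- The Section 6.5 list is permissive. Its layout in the extracted text does not make certain which conditions fall under the escalation clause. It still has some weight, because Section 5.4 ends dosing at treatment failure.
- The effect on mutation testing is small. Section 5.4.1 separately calls for a test whenever optimal response is lacking, and Section 7.1.1.2 has its own list of triggers.
- A site that escalated every eligible patient above threshold would breach neither statement. That is an observation about compliance and does not favour either rule.

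**Conclusion.** Section 5.4.1 contradicts itself at Month 6, with a weaker tension at Month 3, and no other text resolves it. For a patient above threshold at Month 6 who meets the safety criteria, not escalating is allowed discretion or a deviation depending on the sentence applied. The possible difference is 0 against up to about 24 weeks on an increased dose before Week 48. That figure assumes a first increase at Month 6, treatment continuing to Week 48 and no delay. When the Section 6.5 treatment-failure conditions can apply is also left unclear.

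A reader might go further and infer that the primary result is biased or that power is affected. The documents do not support this. They do not say how many patients will be above threshold at Month 6 or how MMR responds to escalation, and no analysis set, primary-endpoint rule or EFS rule uses the condition. The consequence is inconsistent site conduct and inconsistent classification of deviations. It should be fixed, but it is not an analysis error.

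**What to change.** Issue a clarification letter or protocol amendment that:

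- reconciles the Month 3 and Month 6 paragraphs of Section 5.4.1 with its definition of lack of response, stating at which visit an increase is mandatory, at which it is discretionary, and what triggers it at Month 6;
- states whether the Month 6 statement covers a patient whose dose was already increased at Month 3;
- corrects the Appendix 2 reference in the Month 6 paragraph;
- confirms that Sections 6.2, 6.5 and 7.1.1 still follow from the reconciled text.

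Which rule applies is for the sponsor's clinical team to decide; this review takes no position. The cost is the letter or amendment and notification of sites. No analysis needs to change.

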5.4.2. Dosing Interruptions and Dose Reductions

The dose of bosutinib may be interrupted and/or reduced for the toxicities described below.

For bosutinib, a dose reduction from 400 mg QD to 300 mg QD is permitted. If a patient requires a second dose reduction from 300 mg QD to 200 mg QD, the investigator should contact the sponsor to determine if the patient may continue on treatment at a lower dose. The second dose reduction must be approved by the sponsor and will only be considered if the patient in question displays optimal response to bosutinib treatment at the time point at which the dose reduction is being considered. Patients should remain on the 200 mg dose for a maximum of 4 weeks or until the toxicity resolves, whichever is sooner, in line with the dose reduction and dose escalation guidelines. The dose may then be re-escalated following the escalation guidelines. Any patient on the 200 mg dose with ongoing toxicity after the 4-week time point will be discontinued from treatment and will continue with Long-Term Follow-Up evaluations. Dose reductions of bosutinib below 200 mg QD will not be permitted.

If the investigator and the sponsor decide that it is not in the best interest of the patient to remain on treatment at a dose lower than 300 mg QD, the patient will be discontinued from treatment and will continue with Long-Term Follow-Up evaluations.

Once the dose has been reduced for a patient, patients should remain on that dose unless the toxicity resolves (Grade ≤ 1). In that case, the dose may be escalated to the previous starting dose.

Management of Non-Hematologic Treatment-Related Toxicities

The management of non-hematologic treatment-related toxicities is summarized in [Table 2](#).

Patient instructions for the management of diarrhea are presented in [Appendix 6](#).

Table 2. Management of Non-Hematologic Treatment-Related Toxicity

Adverse Event	Action
Elevated liver transaminases	If elevations in ALT, AST >5× institutional ULN occur, bosutinib should be interrupted until recovery to ≤ 2.5×ULN and may be resumed at 400 mg QD thereafter. If recovery takes longer than 4 weeks, discontinuation of bosutinib should be considered. If transaminase elevations ≥3×ULN occur concurrently with bilirubin elevations >2×ULN and alkaline phosphatase <2×ULN, bosutinib should be discontinued.
Diarrhea	For Grade 3/4 diarrhea, bosutinib should be interrupted and may be resumed at 400 mg QD upon recovery to Grade ≤ 1.
Grade 1	Current dose level.
Grade 2	For persistent clinically relevant toxicity ^b not responding to optimal management: Temporarily interrupt treatment, and reintroduce at the same dose or reduce dose by 1 level upon recovery to Grade ≤1 within 4 weeks of stopping test article.
Grade 3 ^a	For persistent clinically relevant toxicity ^b not responding to optimal management: Withhold treatment, then dose reduce by 1 level upon recovery to Grade ≤1 within 4 weeks of stopping test article. If recovery takes longer than 4 weeks, the investigator should contact the sponsor to determine if the patient may continue on treatment.
Grade 4 ^a	Withhold treatment. Investigator and sponsor to review to determine if patient may continue on treatment with appropriate dose reduction.

Abbreviations: ALT = alanine aminotransferase; AST = aspartate aminotransferase; QD = once daily; ULN = upper limit of normal

- a. For patients requiring dose reduction due to toxicity, who have been free of the toxicity (Grade ≤1) for at least 1 month and are otherwise tolerating study drug, the investigator may choose to re-escalate dose by 1 dose level back to starting dose.
 b. Persistent Clinically Relevant Toxicity is defined as - symptoms of toxicity which, despite optimal medical management, persist for ≥14 days (“persistent”) and cause sufficient symptoms or signs of illness in the patient to warrant further intervention, eg, dose adjustment (“clinically relevant”).

Patients with Grade 3 non-hematological toxicity which does not respond to optimal management, will be managed by withholding treatment followed by dose reduction by 1 level upon recovery to Grade ≤1. If, upon re-challenge at a reduced dose, the patient remains free of toxicity (Grade ≤1) for at least 1 month, the investigator may choose to re-escalate the dose by 1 level back to the starting dose. If, subsequently, the patient fulfills the criteria for dose escalation due to suboptimal response (detailed in Section 5.4.1), this will be permitted for vomiting, nausea, abdominal pain, rash, headache, myalgia, or fatigue provided that the toxicity is Grade ≤2 is manageable with supportive therapy. All other non-hematological toxicities should be Grade ≤1 for dose escalation.

Patients fulfilling criteria for dose escalation due to suboptimal response, but also exhibiting elevated liver transaminases as described in Table 2, will not be dose escalated at this time, and will be managed according to the instructions in Table 2.

In line with the Summary of Product Characteristics²⁶ for bosutinib, caution is recommended in patients with previous history of pancreatitis and in patients with increased serum lipase in conjunction with abdominal symptoms. Therefore, for study patients with previous history of pancreatitis, in the event of elevation of lipase level >1.5 × ULN (ie, CTCAE Grade 2 or above), bosutinib treatment should be interrupted immediately, and additional investigations and lipase monitoring should be performed to exclude pancreatitis. In addition, for any study

patient with elevation of lipase level $>1.5 \times$ ULN in conjunction with abdominal pain, bosutinib treatment should be interrupted, and similar investigations to exclude pancreatitis performed. Bosutinib treatment may be restarted only once pancreatitis is excluded and lipase levels return to CTCAE Grade ≤ 1 .

Management of Hematologic Treatment-Related Toxicities

Guidelines in Table 3 pertain to patients with normal or higher than normal blood counts or patients who have achieved CHR.

Table 3. Management of Hematologic Treatment-Related Toxicity

Adverse Event	Action
Grade 1	Current dose level
Grade 2	Current dose level
Grade 3 ^a	Withhold treatment: If recovered to Grade ≤ 2 within 2 weeks of treatment hold: re-introduce study drug at same dose. If recovered within 4 weeks of treatment hold: reduce study drug by 1 dose level. At subsequent occurrences of Grade 3 toxicity, dose must be reduced upon recovery to Grade ≤ 2 . If recovery takes longer than 4 weeks, the investigator should contact the sponsor to determine if the patient may continue on treatment.
Grade 4 ^a	Withhold treatment. Investigator and sponsor to review to determine if patient may continue on treatment with appropriate dose reduction.

a. For patients requiring dose reduction due to toxicity, who have been free of the toxicity (Grade ≤ 1) for at least 1 month and are otherwise tolerating study drug, the investigator may choose to re-escalate dose by 1 dose level back to starting dose

Patients fulfilling criteria for dose escalation due to suboptimal response, but also exhibiting Grade 2 hematologic treatment-related toxicity, will be eligible for dose escalation; however, if hematologic toxicity increases to Grade 3/4 after dose escalation, the patient will be managed as per the instructions for Grade 3/4 hematological toxicities in Table 3.

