8.3. Severity Assessment

GRADE	Clinical Description of Severity
0	No change from normal or reference range (This grade is not included in the Version 4.03 CTCAE document but may be used in certain circumstances.)
1	MILD adverse event
2	MODERATE adverse event
3	SEVERE adverse event
4	LIFE-THREATENING consequences; urgent intervention indicated
5	DEATH RELATED TO adverse event

Note the distinction between the severity and the seriousness of an AE. A severe event is not necessarily an SAE. For example, a headache may be severe (interferes significantly with the patient's usual function) but would not be classified as serious unless it met one of the criteria for SAEs, listed above.

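### After raised transaminases or Grade 3/4 diarrhea, Table 2 permits restart at a fixed 400 mg QD, which is a one-level increase when the event occurred at 300 mg

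*Protocol*

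**What the plan says.** The starting dose is 400 mg QD. Table 1 (Protocol Section 5.4) has two levels above it (500 and 600 mg) and two below (300 mg, and 200 mg with sponsor approval).

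Table 2 (Section 5.4.2) opens with two rows for named events:

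- **Transaminases.** ALT or AST above 5 times ULN leads to interruption until recovery to 2.5 times ULN or less, after which bosutinib "may be resumed at 400 mg QD thereafter".
- **Diarrhea.** "For Grade 3/4 diarrhea, bosutinib should be interrupted and may be resumed at 400 mg QD" on recovery to Grade 1 or less.

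Rows by grade follow:

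- **Grade 2**, if persistent and clinically relevant: "reintroduce at the same dose or reduce dose by 1 level upon recovery".
- **Grade 3**, under the same condition: "Withhold treatment, then dose reduce by 1 level upon recovery to Grade" 1 or less.
- **Grade 4**: withhold, then "Investigator and sponsor to review to determine if patient may continue on treatment with appropriate dose reduction".

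For hematologic toxicity, the Grade 3 row of Table 3 is also relative: "re-introduce study drug at same dose" after quick recovery, otherwise one level down.

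Footnote a, attached to the Grade 3 and Grade 4 rows, and the paragraph below Table 2 allow return to the starting dose only after at least one month free of the toxicity. Earlier in the section, a general sentence covers patients on a reduced dose whose toxicity has resolved: "In that case, the dose may be escalated to the previous starting dose".

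**The concern.** A restart rule after a severe toxicity would normally keep the patient at the dose that caused it or go lower. The grade rows of Table 2 and the Grade 3 row of Table 3 do this. The two named-event rows give an absolute dose, so their effect depends on where the patient was when the event occurred. At 300 mg they permit a step up.

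A second, smaller question is which row governs when an event falls under two. Grade 4 diarrhea fits both the diarrhea row and the Grade 4 row. Section 8.3 describes Grade 4 as "LIFE-THREATENING consequences; urgent intervention indicated", so it matters whether sponsor review and a dose reduction are needed.

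At stake is the safety of patients already on a reduced dose, and consistency between sites treating the same event.

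**Working it through.** The plan states no figure to reproduce. The check applies the Table 2 wording to each dose level in Table 1.

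**Step 1. Effect of the fixed dose.** Change = 400 mg minus dose at onset; percentage = change divided by dose at onset.

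| Dose at onset | Restart at 400 mg | One level down, for comparison |
|---|---|---|
| 600 mg | -200 mg (-33%) | 500 mg |
| 500 mg | -100 mg (-20%) | 400 mg |
| 400 mg | 0 | 300 mg |
| 300 mg | +100 mg (100/300 = +33%) | 200 mg, sponsor approval |
| 200 mg | +200 mg (+100%) | not permitted |

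The fixed dose equals one level down only for an event at 500 mg. At the starting dose it is no reduction. At 300 mg it is an increase.

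**Step 2. Is the 300 mg case realistic?** Yes. Reduction from 400 to 300 mg needs no sponsor approval, and a patient may stay there. The 200 mg case is remote: it requires sponsor approval and an optimal response, lasts at most 4 weeks, and ongoing toxicity after that means stopping.

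**Step 3. Does other text prevent the increase?**

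- The paragraph below Table 2 requires a one-level reduction, and a month free of toxicity before re-escalation, for Grade 3 non-hematologic toxicity that does not respond to optimal management. Where it applies, it points the other way from the named rows. It does not reach Grade 3 diarrhea that resolves promptly with management.
- Footnote a is attached to the Grade 3 and Grade 4 rows, not to the two named rows.
- The general sentence on returning to the starting dose gives no waiting time, so it does not supply a cap.
- Section 5.4.1 requires successful re-challenge at the lower dose before escalation after Grade 3/4 toxicity. That rule concerns escalation for inadequate response. It shows intent but does not govern restarts.
- The SAP contains no dosing rule.

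**Step 4. Overlapping rows, for diarrhea at 400 mg.**

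- Grade 4: the diarrhea row allows 400 mg without review. The Grade 4 row calls for joint review and a reduction, so 300 mg or less ((400 - 300)/400 = at least 25% lower).
- Grade 3 that is persistent under footnote b (at least 14 days despite optimal management, and clinically relevant): 400 mg under the diarrhea row, 300 mg under the Grade 3 row.
- Grade 3 that is not persistent: no conflict.

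The transaminase row has no upper limit, so a Grade 4 elevation also falls under two rows. The grade rows are not labelled as applying to other toxicities, and no sentence gives precedence.

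**The case against.** The strongest reply has four parts.

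1. **The wording permits and does not instruct.** Interruption and recovery come first, and an investigator may choose a lower dose. This stands. A reader might infer that the protocol forces an increase, or one without a pause; it does neither. But 400 mg is the only restart dose these rows name, and they do not tell a site that it is too high after an event at 300 mg.

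2. **Other text already limits the restart.** This stands in part. The paragraph below Table 2 is mandatory and not limited by event type, and footnote a could reasonably be applied to someone already reduced for toxicity. A reader might infer that nothing at all limits the restart dose; the documents do not support that. These provisions cover only some cases, however, and do not override the named rows.

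3. **Specific rows take precedence over general ones.** This is an ordinary reading and may be what was meant. It would settle the overlap, making that a matter of stating precedence. It would leave the increase at 300 mg in place.

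4. **The general sentence is not a contradiction.** A reader might infer that return to the starting dose on resolution conflicts with the one-month wait. The two can stand together: the sentence as the general rule, which also covers Grade 2 reductions, and the wait as the rule after Grade 3/4 events. Imposing the wait on every reduction would also clash with the 4-week limit at 200 mg.

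Section 1.2.3 reports that in the BELA study 91% of bosutinib patients with Grade 3/4 transaminase elevations were re-challenged, 80% of them successfully. The re-challenge dose is not given, so this does not show that a higher dose is safe.

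**Conclusion.** The point holds for the two named rows. For an event at 300 mg, the wording permits a restart one level higher, +33%, after recovery but with no toxicity-free period at the lower dose. This is out of line with the relative rules around it and should be corrected. The overlap for Grade 4 events and persistent Grade 3 diarrhea is real but secondary, because it needs only a statement of how the rows combine.

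The conclusion rests on reading the rows as written and on 300 mg being an ordinary planned level. It does not depend on an event count. The documents give no rate of these events at 300 mg, so no number of patients can be supported; since the case needs a second toxicity after a reduction, it is probably few.

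A reader might infer that the trial's statistical conclusions are affected. They are not: the primary test, alpha and sample size do not depend on the restart rule, and the dose summaries in SAP Section 6.5.3 are descriptive.

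**What to change.** 1. **Main change.** In both the transaminase and diarrhea rows of Table 2, allow restart at 400 mg QD or at the dose at onset, whichever is lower.

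2. **Secondary clarification.** State that Grade 4 diarrhea and Grade 4 transaminase elevation also need the joint review and appropriate dose reduction of the Grade 4 row. State that diarrhea meeting the persistence condition of the Grade 3 row is reduced by one level. In every case the restart dose should be no more than 400 mg; without that ceiling, one level down from 600 mg would be 500 mg, above what the diarrhea row now allows. Reduction to 200 mg stays subject to sponsor approval and the 4-week limit.

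3. **Leave the general sentence on returning to the starting dose as it is.** If a waiting time is wanted there, confine it to reductions to 300 mg after Grade 3/4 toxicity, so that it does not collide with the 4-week limit at 200 mg.

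**Cost.** A protocol clarification, site re-training, and slightly lower dose intensity in a few patients. A patient at 300 mg with Grade 4 or persistent Grade 3 diarrhea would need sponsor approval for 200 mg or would stop, as the grade rows already imply. No extra patients, visits or tests are needed.
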